4.3. Removal of Subjects from Treatment

In accordance with the current revision of the Declaration of Helsinki and other applicable regulations, a subject has the right to withdraw from the study at any time and for any reason without prejudice to his or her future medical care by the physician or at the institution. A subject's participation may also be discontinued by the Investigator or Sponsor due to compliance, safety, or other administrative reason (see also [Section 6.2.12](#)).

The subject **must** be discontinued from the study for the occurrence of an unacceptable toxicity, including any of the following:

- ALT or AST $> 8 \times$ ULN; ALT or AST $> 5 \times$ ULN for > 2 weeks; or ALT or AST $> 3 \times$ ULN and total bilirubin $> 2 \times$ ULN or INR > 1.5 ; or ALT or AST $> 3 \times$ ULN with the appearance of worsening of fatigue, nausea, vomiting, right upper quadrant pain or tenderness, fever, rash, or eosinophilia.

Refer to [Section 3.1.4](#) for details regarding follow-up after early discontinuation. Additional care and treatment will be provided to subjects once study discontinuation, including any required follow-up visits for resolution for study-related AEs, is completed.

Subjects who withdraw from the study treatment and/or study for a reason prior to Day 21 will be replaced.

5. TREATMENTS ADMINISTERED

Neftlamapimod 40 mg capsule(s) or matching placebo capsules will be administered orally, BID with a meal or snack for 24 weeks. Doses should be taken within 30 minutes following a meal or snack (i.e., breakfast and dinner) no less than 8 hours apart and at approximately the same times each day throughout the study.

All subjects will receive matched (by size and color) capsules that contain 40 mg neftlamapimod or placebo, respectively.

The first dose of study drug and the morning dose on Day 21 will be administered at the clinical site.

The Investigator or other designated, qualified site personnel should review dosing instructions with the subject. Subjects will be instructed to return all study containers, regardless of whether empty or containing unused study drug.

5.1. Packaging and Labeling

EIP Pharma will supply placebo or neftlamapimod capsules on an individual subject basis.

Both neftlamapimod and placebo capsules are opaque in color. Label details will be in accordance with local and national requirements.

5.2. Study Drug Supply, Storage, and Handling

Study drug will be supplied to the site on a per-subject basis.

Capsules will be supplied in blister cards, which each blister card containing 16 capsules (i.e., 1-week supply of study, with two extra capsules). The blister cards will be packaged in cartons containing a 3-week supply of study drug (i.e., 3 blister cards per carton).

Neftlamapimod capsules should be stored at 59 to 86°F (15–30°C; controlled room temperature), and should not be exposed to heat in excess of 86°F (30°C) or to high humidity.

While at the clinical site, study drug access should be limited to the Investigator and other qualified site personnel.

5.3. Drug Accountability, Disposal, Return, or Retention of Unused Study Drug

The site designated pharmacist or other qualified personnel will document receipt from Sponsor, dispensing to subjects, and return to site from subject on the drug accountability log(s).

Subjects will be instructed to return all blister packs, regardless of whether empty or containing unused study drug. EIP Pharma or designee will review accountability records throughout the conduct of the study.

The site should maintain all study drug containers (used and unused) until final review of accountability is conducted by the EIP Pharma or designee, and instructions regarding return or disposal, as applicable, are provided.

5.4. Method of Assigning Subjects to Treatment Group

After subjects have completed Screening Visit 2 and are deemed eligible, they will be randomized in a blinded manner to either placebo or neflamapimod treatment utilizing a central Interactive Web Response System (IWRS). Study drug for the entire 24-week period will then be sent on a per subject basis to the site. Randomization will be stratified by 1) background AD-specific therapy (cholinesterase inhibitor or memantine versus no cholinesterase inhibitor or memantine); and 2) CDR-Global Score of 0.5 versus 1.0.

5.5. Study Blinding and Breaking the Blind

Subjects and site personnel associated with study conduct will be blinded to treatment assignment.

During the conduct of the study, the blind may be broken on an individual subject basis in the event of an emergency where it is necessary for the Investigator to know which treatment the subject is receiving before the subject can be treated. The code may also be broken if someone not in the study uses study drug (e.g., if a child in the participant's household takes study drug, the blind may be broken to determine treatment for the child.)

When it is necessary to break the blind, the researcher may unblind the treatment immediately (i.e., without prior notice to the medical monitor, sponsor, or other) but must notify the Institutional Review Board (IRB)/Independent Ethics Committee (IEC) and the Medical Monitor and/or Sponsor as soon as possible, preferably by telephone and then in writing, regarding the necessity of code breaking. When possible, the Medical Monitor should be contacted to discuss reasons for breaking the blind.

If the code is broken for a subject, this must be documented in the electronic case report form (eCRF) and source documents, together with the reasons for breaking the code.

5.6. Dose Modification for Toxicity

No dose modifications are permitted during the study. If a subject is unable to tolerate the assigned study drug dose then the subject should be discontinued from study drug treatment ([Section 4.3](#)).

5.7. Prior and Concomitant Therapy

Any medications taken from Screening through Follow-up Visit, including all prescription and over-the-counter medications as well as supplements, will be documented in the subject's source document and in the eCRF.

At study entry, any subject taking a drug for AD (e.g., donepezil or other cholinesterase inhibitors or memantine) must have been on a stable dose for at least 2 months (refer to [Section 4](#)). Furthermore, the dose must remain unchanged during the study, unless required for management of AEs.

While drug-drug interaction studies have not been conducted, in vitro testing indicates that neflamapimod is metabolized by oxidation in the liver by the CYP system (combination of CYP3A4 and CYP2C19 isozymes). Until the metabolism is better characterized, **concomitant strong inhibitors of CYP3A4 are prohibited and strong inducers of CYP3A4 should be used with caution in subjects receiving neflamapimod**, as the use of such drugs in could impact neflamapimod metabolism in subjects who have an underlying CYP2C19 genotypic variant that impacts activity of that CYP2C19. Subjects will be tested for CYP2C19 genotype at baseline to assess any differences in neflamapimod levels and effect (see [Section 6.2.5](#)).

The following medications are prohibited during study participation:

- Strong CYP3A4 inhibitors (see [Table 5-1](#)).
- Any other investigational drug. If a subject has previously participated in a study of an investigational drug, last dosing must have occurred 3 months or 5 half-lives of the investigation drug, whichever is longer, before enrollment in this study.
- Any anti-tumor necrosis factor-alpha therapy.
- Typical and atypical antipsychotics.

The Medical Monitor should be contacted with any questions regarding concomitant use of medications that are thought to modulate CYP3A4 activity.

Table 5-1: CYP3A4 Inhibitors

Strong Inhibitors ≥5-fold increase in AUC or >80% decrease in CL	Moderate inhibitors ≥2 but <5-fold increase in AUC or 50-80% decrease in CL	Weak inhibitors ≥1.25 but <2-fold increase in AUC or 20-50% decrease in CL
boceprevir cobicstat clarithromycin conivaptan danoprevir/ritonavir diltiazem elvitegravir/ritonavir grapefruit juice idelalisib indinavir/ritonavir itraconazole ketoconazole lopinavir/ritonavir nefazodone nelfinavir paritaprevir/ritonavir/ombitasvir posaconazole ritonavir saquinavir/ritonavir telaprevir tipranavir/ritonavir troleandomycin voriconazole	aprepitant cimetidine ciprofloxacin clotrimazole crizotinib cyclosporine dronedarone erythromycin fluconazole fluvoxamine imatinib tofisopam verapamil	chlorzoxazone cilostazol fosaprepitant istradefylline ivacaftor lomitapide ranitidine ranolazine tacrolimus ticagrelor

Table 5-2: CYP3A4 Inducers

Strong Inducers ≥80% decrease in AUC	Moderate Inducers 50-80% decrease in AUC	Weak Inducers 20-50% decrease in AUC
carbamazepine enzalutamide mitotane phenytoin rifampin St. John's wort	bosentan efavirenz etravirine modafinil	armodafinil rufinamide

Abbreviations: AUC, area under the concentration-time curve

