To further understand the impact of neflamapimod on episodic memory as assessed by WMS, an analysis of the relationship between plasma drug (neflamapimod) concentrations and outcome on WMS immediate and delayed recall tests was conducted. Using a standard linear pharmacokinetic-pharmacodynamic (PK-PD) regression model, a highly significant positive correlation was established between plasma drug levels and level of improvement at Day 84 in combined WMS-immediate and delayed recall (p=0.001). Moreover, plasma drug levels explained 70% (i.e., $r^2=0.70$) of the variance in change (improvement) from baseline to end-of-treatment. These statistics strongly argue that the improvement seen in episodic memory in this study was primarily due to neflamapimod treatment, and not due to chance or practice effects. In addition, the concentration dependency of the effects on episodic memory in the plasma drug levels achieved with the dose range of 40 mg to 125 mg that there is no rationale for going to lower doses, as they would simply lead to lower efficacy; while the difference in plasma drug concentrations achieved with the two doses, and therefore effect on episodic memory, were not substantial.

In Study 303 (6-week study in Los Angeles), the HLVT-R was utilized to assess episodic memory. In this test, 12 specific words from a list are provided verbally, and subject asked to recall as many words as possible. Two scores are calculated:

- Total (Immediate) Recall Score (0-36): combined score of 3 consecutive trials immediately following provision of words.
- Delayed Recall Score (0-12): Number of words recalled when subject is asked 20-25 minutes after initial trials to recall as many of the words originally provided.

A strength of the HVLT-R is that 5 different validated versions exist that incorporate different set of words. Due to the use of these different versions during the course of a clinical study, there is essentially no practice effect ([Benedict, et al, 1998](#)) with repeated administration.

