3.2.1.1. Efficacy Considerations

The 40 mg BID regimen was chosen because PK-PD modeling (plasma drug concentration response) correlations indicated a plasma drug concentration dependency on the effects on episodic memory that argues against going to lower doses and only modest further increase in efficacy with utilizing 125 mg dose level, while the loss of an amyloid plaque load effect at 125 mg dose level provides a specific reason not to increase the dose above 40 mg. The PK-PD modeling was also consistent with the *in vitro* potency of the drug and predicted doses for optimal cognitive effects based on pre-clinical studies (Alam, 2015). Moreover, the 40 mg dose level provides an appropriate safety margin relative to findings in chronic toxicology findings in the dog (Section 3.2.1.2).

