12. Male subjects with female partners of child-bearing potential who are unwilling or unable to adhere to contraception requirements ([Section 5.8](#))
13. Female subjects who have not reached menopause or have not had a hysterectomy or bilateral oophorectomy/salpingo-oophorectomy.
 - If a female subject reached menopause within the previous year, a pregnancy test must be performed during Screening and the subject must be willing to adhere to the contraception requirements specified in the protocol. Such subjects with a positive urine or serum pregnancy test are not eligible for study participation.
14. Requires concomitant use of strong cytochrome P450 (CYP) 3A4 inhibitors or anti-tumor necrosis factor-alpha therapies during study participation (see [Section 5.7](#)).

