6.2.5. Genotyping and Apolipoprotein E4 Testing

A blood sample will be collected from all subjects at Visit 3 (Day 1) for CYP2C19 genotyping; such testing is mandatory. The CYP2C19 gene encodes for a drug metabolizing enzyme that accounts for approximately half the metabolism of neflamapimod. (The other is the CYP3A4 enzyme). As there are known polymorphisms in CYP2C19, particularly in Asian populations, that reduce the function of this enzyme, the PK profiles in individual subjects may be impacted CYP2C19 genotype (Fricke-Galindo et al, 2016). PK profiles will be obtained in all subjects and correlated against CYP2C19 genotype (see Section 6.2.8 and Section 8.4). An aliquot of blood from this sample may also be used for measurement of apolipoprotein E4; such testing is optional. Results will be available to study sites and may be discussed with the subjects only after the clinical study report has been completed.

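### Strong CYP3A4 inducers are allowed with caution at a fixed dose; prohibiting them in all subjects is a cheap, small improvement

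*Protocol*

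**What the plan says.** - **Inhibitors and inducers are treated differently.** Protocol 5.7 bars strong CYP3A4 inhibitors outright. For inducers it says that "strong inducers of CYP3A4 should be used with caution in subjects receiving neflamapimod". The 5.7 list of prohibited medications has no inducers. Exclusion 14 (synopsis and 4.2) reads "Requires concomitant use of strong cytochrome P450 (CYP) 3A4 inhibitors or anti-tumor necrosis factor-alpha therapies during study participation" and does not name them either.
- **What counts as strong.** Table 5-2 heads the column "Strong Inducers ≥80% decrease in AUC" and lists carbamazepine, enzalutamide, mitotane, phenytoin, rifampin and St. John's wort.
- **Evidence and metabolism.** Section 5.7 opens its reasoning with "While drug-drug interaction studies have not been conducted" and ties the worry to subjects with a CYP2C19 variant. Section 6.2.5 states: "The CYP2C19 gene encodes for a drug metabolizing enzyme that accounts for approximately half the metabolism of neflamapimod". It names CYP3A4 as the other enzyme.
- **Dose.** Section 5.6: "No dose modifications are permitted during the study".
- **Exposure rationale.** Section 1.3 says "there is no rationale for going to lower doses, as they would simply lead to lower efficacy". Section 3.2.1.1 refers to "a plasma drug concentration dependency on the effects on episodic memory that argues against going to lower doses".
- **What is already in place.** All medications and supplements are recorded, and the Medical Monitor takes questions about drugs that modulate CYP3A4 (5.7). PK is sampled on Days 21, 42 and 84 (6.2.8). Population PK and a post hoc PK/PD model are planned (8.4; SAP 6.11 for the population PK). A clinical pharmacologist reviews PK every three months (8.7).

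**The concern.** The protocol argues against going below 40 mg twice daily, yet admits subjects on drugs that its own table defines by a large fall in AUC, with no dose adjustment to compensate. Caution is not defined: no washout, stability rule or threshold for action is attached to it.

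The reason given in 5.7 is also narrower than the pharmacology in 6.2.5. If CYP3A4 carries about half of clearance, inducing it lowers exposure in everyone. A site could not single out variant carriers at entry in any case, because the genotype sample is drawn on Day 1, after eligibility is settled and treatment assigned (6.2.5, 5.4). Nor, under blinding (5.5), could it apply the caution by arm.

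At stake is some loss of drug effect in active-arm users with no counterpart on placebo, so any influence on the primary comparison is toward no difference. And because use is permitted, it is not the prohibited-medication violation of 9.9. It need not be logged as a deviation, so the per-protocol review in SAP 6.1.3, which works from deviations, may never consider these subjects.

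**Working it through.** **1. The plan's own power.** Inputs: 76 per arm, effect sizes (ES) 0.46 and 0.53 (Protocol 8.2, SAP 4), two-sided 0.05 (SAP 6.10), 1:1 allocation. A two-sample t-test with the noncentral t gives 80.4% at ES 0.46 and 90.1% at ES 0.53. The stated 80% and 90% reproduce.

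**2. Exposure in a user.** Let s be the CYP3A4 share of clearance (about 0.5, from 6.2.5) and g the CYP2C19 activity (1 = normal). An AUC fall of 80% for a drug cleared only by CYP3A4 means that CYP3A4 clearance rises 1/0.20 = 5-fold. Relative to an uninduced subject with normal genotype:

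AUC ratio = 1 / [g(1 − s) + 5s]

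| CYP2C19 activity g (s = 0.5) | Uninduced | Induced | Induced ÷ own uninduced |
|---|---|---|---|
| 1 (normal) | 1.00 | 1/3.00 = 0.33 | 0.33 |
| 0.5 | 1.33 | 1/2.75 = 0.36 | 0.27 |
| 0 | 2.00 | 1/2.50 = 0.40 | 0.20 |

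For g = 1, the ratio is 1/2.6 = 0.38 at s = 0.4 and 1/3.4 = 0.29 at s = 0.6. Under linear PK, 0.33 is like 40 × 0.33 ≈ 13 mg twice daily. Variant carriers lose more relative to themselves, but the lowest absolute exposure is in normal-genotype subjects. This assumes linear clearance, induction at the class threshold and no induction of CYP2C19.

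**3. Dilution of the treatment effect.** Let u be the share of the active arm on a strong inducer. The documents give no rate, so u = 0.5–5% is assumed, with 5% as an upper value. If effect is proportional to exposure, a user keeps one third of it:

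ES_eff = ES × (1 − 0.667u)

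| u | Expected users among 76 | ES_eff from 0.46 | Power | Power from ES 0.53 | n per arm for 80% at ES 0.46 |
|---|---|---|---|---|---|
| 0 | 0 | 0.4600 | 80.4% | 90.1% | 75.2 |
| 0.5% | 0.4 | 0.4585 | 80.2% | 89.9% | 75.7 |
| 1% | 0.8 | 0.4569 | 79.9% | 89.7% | 76.2 |
| 2% | 1.5 | 0.4539 | 79.4% | 89.3% | 77.2 |
| 5% | 3.8 | 0.4447 | 77.7% | 88.1% | 80.4 |

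In total subjects, 2 × (n − 76) is negligible up to 1% use, about 2 at 2% and about 9 at 5%.

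**4. Bounds.** If induction removed the whole effect, ES_eff = 0.46(1 − u), and power is 80.05%, 79.65%, 78.85% and 76.32% at the four rates. If effect does not depend on exposure in this range, the loss is zero. Varying s from 0.4 to 0.6 at 5% use moves power only between 78.0% and 77.6%.

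**The case against.** The strongest case against is that this is a drafting preference. At 0.5–2% use the loss is one power point or less against a rounded 80%, and about 0.4 to 1.5 active-arm subjects are involved. Exclusions 3, 5, 6 and 8 already remove many likely users. The one-third figure applies a class threshold to a drug with no interaction study, and proportionality below 40 mg is assumed. The rationale in 1.3 and 3.2.1.1 justifies the assigned dose; it does not address co-medication. Section 5.7 does recognise inducers, its caution covers every treated subject, and its mention of variants is defensible because the within-subject fall is largest there. The stricter inhibitor rule has a plausible safety basis: transaminase increases at higher plasma levels (3.2.1.2).

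Most of that stands and sets the grade. It does not remove the point: existing exclusions leave gaps (St. John's wort is named in no exclusion, the seizure criterion reaches back only 5 years, prostate cancer without significant progression is allowed), and the loss runs one way.

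Two stronger readings are tempting. The first is that later inducer starts would go unseen, because the initial PK-PD analysis in SAP 6.12 uses Day 21 concentrations. The documents do not support this: medication records, the Day 42 and 84 samples, and the population PK and PK/PD work (8.4, SAP 6.11) can all show them. The three-monthly PK review (8.7) could show low levels too, though that reviewer does not see concomitant medications. The second is that SAP 6.1.3 already guarantees a per-protocol review blind to arm. It requires sponsor review before database lock but says nothing on blinding, and 5.5 names only subjects and site personnel as blinded.

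**Conclusion.** The point holds as a low-cost improvement to consider. The rule on strong inducers sits poorly with the protocol's own metabolism and dose reasoning, and the exposure loss per treated user could be large: to about 0.33 of usual AUC in a normal-genotype subject, under the class threshold and linear clearance.

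A reader might infer that the sample size is inadequate or the primary result threatened. The documents do not support that. The stated power reproduces, the rate of use is unknown and probably low, and at 0.5–2% use the loss at ES 0.46 is 0.2 to 1.0 point under proportionality. It is 2.7 points at 5%, and zero if effect does not depend on exposure.

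The gain is mainly at entry, since a medically needed start after randomization must still be tolerated. Confidence is medium: the arithmetic is firm, but the rate of use, the size of induction and the exposure–effect relation below 40 mg are all assumed.

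**What to change.** 1. **Protocol 5.7.** Prohibit strong CYP3A4 inducers along with strong inhibitors, in all subjects and whatever the CYP2C19 genotype. Add them to the prohibited list with reference to Table 5-2, naming St. John's wort.
2. **Exclusion 14 (synopsis and 4.2).** Add inducers beside inhibitors. Candidates who medically need a strong inducer are excluded. Those on a non-essential one may enter after a washout set by the sponsor's clinical pharmacologist, which must fit the 42-day screening window (3.1.1). The documents give no figure for its length.
3. **Protocol 9.9.** State that a medically needed start after randomization is a protocol violation but not by itself a reason to withdraw the subject, and that scheduled assessments continue. Without this, the sponsor could withdraw the subject (9.9, 6.2.12), and missing efficacy data are not imputed (SAP 6.10).
4. **SAP 6.1.3.** Such a subject stays in the Efficacy Population as randomized and is considered for per-protocol exclusion. Add a short statement that this review is done blind to treatment arm.

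**Cost.** Six short edits (two in 5.7, exclusion 14 in two places, one each in 9.9 and SAP 6.1.3) and no new data. At 0.5–5% use, 0.005 × 152 = 0.8 to 0.05 × 152 = 7.6, or about 1 to 8 places across both arms, go to other candidates or wait for a washout. A new inducer start becomes a protocol violation, with an express retention rule that other prohibited drugs do not have.

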5.8. Contraception and Pregnancy

This section should be read in conjunction with the selection criteria that relate to age and contraception:

- Inclusion criterion #1 ([Section 4.1](#)) and Exclusion criteria #12 and #13 ([Section 4.2](#))

No signs of embryo-fetal toxicity or teratogenic effects of neflamapimod were observed in rats. Testing in rabbits was not performed due to lack of exposure following administration of the neflamapimod formulation. No human studies of effects of neflamapimod on conception, pregnancy, or lactation have been performed. Females should not be exposed to neflamapimod if pregnant, breastfeeding, or attempting to conceive. The following guidelines for contraception should be followed from before first dose on Day 1 through 91 days following the last dose of study drug:

Female subjects of child-bearing potential (have not experienced menopause and have not had a hysterectomy or bilateral oophorectomy/salpingo-oophorectomy) are not eligible for the study. Female subjects who have experienced menopause within the previous year must have a negative pregnancy test during Screening and must use at least 1 of the following contraceptive methods: complete abstinence regardless of menstrual cycle timing, contraceptive (oral, transdermal, injectable, or implantable), intrauterine device, or barrier method of contraception.

Male subjects with female partners of child-bearing potential must use at least 1 of the following contraceptive methods: complete abstinence, vasectomy, or barrier method of contraception.

Pregnancy of a female partner of a male subject (and, although unlikely, in a female subject) should be reported to the Investigator, and, in turn, the pregnancy should be reported to Worldwide Clinical Trials within 24 hours of the Investigator's awareness of the pregnancy. In the unlikely event a female subject becomes pregnant, study drug will be permanently discontinued and the subject will be discontinued from the study.

With proper informed consent (separate pregnancy informed consent form), the subject or partner will be followed through the completion of the pregnancy and outcome of the pregnancy reported, and the infant will be followed for 12 months after birth.

